2.4 Randomization

2.4.1 Treatment randomization

This is an open-label study with a single arm, and all eligible subjects will receive the same dose of 3,500 Units of MYOBLOC. No treatment randomization is necessary.

2.4.2 Injection Technique Assignment

Injections will be guided by external anatomical landmarks or by external anatomical landmarks with ultrasound-guided confirmation. Sites designated as “ultrasound” sites will perform all their injections using external anatomical landmarks with ultrasound-guided confirmation.

2.5 Sample Size Estimation

No sample size estimation is performed for this open-label study. The study plans to enroll a total of 120 to 200 subjects. The sample size, 187 subjects is based on the requirements of the final safety database for approval.

2.6 Efficacy and Safety Measurements

In this study, efficacy will be assessed, using USFR, CGI (severity and change), DIS, DFSS-I, DFSS-S, PGI (severity and change). DFSS-S will be collected through subject’s diaries.

Safety will be assessed through subject early terminations, adverse events, adverse events of special interest (including aspiration, aspiration pneumonia, and choking, dysphagia), dental and oral examination (dental adverse events), physical examination, neurological examination, vital signs, lung functioning assessment, pregnancy test, clinical laboratory evaluations (hematology, chemistry, urinalysis), and concomitant medications as well as Columbia Suicide Severity Rating Scale (C-SSRS).

2.6.1 Effectiveness measures

Several effectiveness measures are assessed over each of the treatment Sessions 1 through 4 at the injection visit (i.e., Day 1, and Weeks 13, 26, and 39), 4 weeks post-injection (i.e., Weeks 4, 17, 30, and 43), 8 weeks post-injection (i.e., Week 8, first treatment session only), and 13 weeks post-injection (i.e., Weeks 13, 26, 39, and 52). Where applicable, the measurement value obtained at pre-injection of each treatment session (i.e., Day 1 and Weeks 13, 26, and 39 for each of the 4 treatment sessions, respectively) is defined as the baseline of the corresponding measures. For the CGI-C and PGI-C, the corresponding severity score observed at pre-injection of each treatment session will be used as the baseline measurement of the corresponding session in analysis.

Unstimulated Salivary Flow Rate (USFR)

The USFR (g/minute) is the salivary flow rate assessed by the independent assessor in an unstimulated state (i.e., at least 1 hour postprandial) at screening, just before the first injection of study drug (Day 1) to establish a baseline salivary flow rate, and at each subsequent study visit (Appendix B of the protocol). To determine USFR at each study

visit, saliva will be collected over a 5-minute collection period using weighing cups

hey will be asked to expectorate, as needed, any saliva that accumulates in their mouth into the pre-weighed cup during the 5-minute collection period.

Although not a rating scale, the same person should conduct this assessment throughout the study to minimize collection technique bias.

Clinical Global Impression of Severity (CGI-S) and Change (CGI-C)

The CGI-S scale is used to record the severity of illness (sialorrhea) on Day 1 (i.e., study baseline) before the first injection of study drug, at each subsequent study visit or, if applicable, at discontinuation from the study. CGI-S will be assessed by a trained assessor on a 7-point scale ranging from “normal” to “among the most extremely ill patients” (Appendix C of the protocol). The CGI-C, used to record change or improvement in illness from baseline (i.e., pre-injection) of each treatment session, will be assessed at each study visit after Day 1 by the assessor on a 7-point scale ranging from “very much improved” to “very much worse” (Appendix C of the protocol). Both CGI scales will be completed independent of the subject’s self-assessment (PGI-S and PGI-C) so neither party knows how the other has rated the scales.

Patient Global Impression of Severity (PGI-S) and Change (PGI-C)

The PGI-S scale will be used by the subject to rate the severity of his/her illness (sialorrhea) on Day 1 (i.e., study baseline) before the first injection of study drug, at each subsequent study visit, or, if applicable, at discontinuation from the study. PGI-S will be assessed on a 8-point scale ranging from “normal” to “among the most extremely ill” (Appendix D of the protocol). The PGI-C will be used by the subject to rate his/her impression of change in symptoms (drooling or sialorrhea) from Day 1 (i.e., study baseline) or just before subject’s most recent injection of study drug to the time of assessment at each study visit. The PGI-C is assessed on a 7-point scale ranging from “very much improved” to “very much worse” (Appendix D of the protocol). Both PGI scales need to be completed independent of the assessor who completes the CGI scales so neither party knows how the other has rated the scales.

Drooling Frequency and Severity Scale (DFSS)

The DFSS is a 2-item scale used to assess the frequency and severity of drooling. The DFSS will have two forms in this study, with one being performed by an independent assessor (DFSS-I) and the other by the subject (DFSS-S). In both forms, drooling severity is assessed on a 5-point scale ranging from 1 (dry, never drools) to 5 (profuse, clothing, hands, tray, objects become wet), whereas drooling frequency is assessed on a 4-point scale ranging from 1 (never drools) to 4 (constantly drools) (Appendix E of the protocol). The total score ranges from 2 to 9 in each DFSS form. The assessor’s initial assessment

of DFSS on Day 1 of Treatment Session 1 should be based on the prior 4 weeks, whereas the subsequent assessments of DFSS should be based on the timeframe since the prior study visit. The independent assessor should not review the subject-rated scales before performing his/her own assessment.

DFSS-S is collected via subject's diary in this study on a daily basis for the first 2 weeks of each treatment session and then weekly for the remainder of the treatment session.

Drooling Impact Score (DIS)

The DIS is a 10-item questionnaire with each item rated by the subject to evaluate the impact of the disorder (sialorrhea) on daily activities (e.g., speech, social activities). For each question, the subject is requested to compare their current status to their last study visit using a 4-point scale ranging from 1 (not at all) to 4 (very much) (Appendix F of the protocol). The DIS total score ranges from 10 to 40. The initial assessment of DIS on Day 1 of Treatment Session 1 before the first injection of study drug should be based on the prior 4 weeks, whereas the subsequent assessments should be based on the timeframe since the prior study visit.

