17 STATISTICS

Detailed methodology for the summary and statistical analysis of the data collected in this study will be documented in a Statistical Analysis Plan (SAP), which will be prepared and finalized before database lock.

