17.9 Statistical Methods for Effectiveness

As subjects will receive multiple single-dose injections, each single-dose injection plus its follow-up period will be considered as a treatment session. Post-injection effectiveness endpoints over each of the treatment sessions include USFR, CGI-C, CGI-S, DFSS-I, PGI-C, PGI-S, DIS, and DFSS-S at the injection visit (i.e., Day 1, Weeks 13, 26, and 39), 4 weeks post-injection (i.e., Weeks 4, 17, 30, and 43), 8 weeks post-injection (i.e., Week 8, first Treatment Session only), and 13 weeks post-injection (i.e., Weeks 13, 26, 39, and 52). The pre-injection time points are Day 1 and Weeks 13, 26, and 39 for each of the consecutive treatment sessions. Missing post-injection measurements will not be imputed, whereas missing measurements at the pre-injection of each treatment session will be imputed by the site-specific average of those subjects who receive the treatment at the corresponding treatment session.

For each treatment session, effectiveness analysis of the treatment response will be performed on USFR change from pre-injection, CGI-C, CGI-S, PGI-C, PGI-S, and DIS change from pre-injection, DFSS-I change from pre-injection, and DFSS-S change from

pre-injection at each of the post-injection time points for the ITT population, using a paired t-test. The ITT population will be grouped into three groups by the actual doses the subject received at each session as the following: low dose (2,500 to 2,999 Units), medium dose (3,000 to 3,499 Units), and high dose (3,500 Units).

In addition, the proportion of treatment responders will be reported for the CGI-C and PGI-C at both pre-injection and post-injection time points over each treatment session. Before the analysis, the CGI-C and PGI-C variables will be dichotomized into 2 categories, with “very much improved” and “much improved” into 1 category and the remaining levels in the other category.

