2.9.1 Effectiveness analysis

As subjects receive multiple single-dose injections, each single-dose injection plus its follow-up period will be considered as a treatment session.

Effectiveness measures obtained over each of the treatment sessions include USFR, CGI-S, CGI-C, DFSS-I, DFSS-S, PGI-S, PGI-C, and DIS at the injection visit (i.e., Day 1, except for CGI-C and PGI-C, and Weeks 13, 26, and 39), 4 weeks post-injection (i.e., Weeks 4, 17, 30, and 43), 8 weeks post-injection (i.e., Week 8, first treatment session only), and 13 weeks post-injection (i.e., Weeks 13, 26, 39, and 52). The injection visit of Day 1 and Weeks 13, 26, and 39 is considered the baseline (or pre-injection), respectively, for each of the consecutive treatment sessions 1 through 4.

For each treatment session, effectiveness analysis of the treatment response will be performed on USFR change from pre-injection, DFSS-I change from pre-injection, and DFSS-S change from pre-injection, CGI-S, CGI-C, PGI-S, PGI-C, and DIS change from pre-injection, at each of the post-injection time points using a t-test.

In addition, the proportion of treatment responders will be reported for the CGI-C and PGI-C at both pre-injection and post-injection time points over each treatment session. Before the analysis, the CGI-C and PGI-C will be dichotomized into 2 categories, with "very much improved" and "much improved" into 1 category and the remaining levels in the other category.

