4.3 Baseline Measures

Descriptive statistics of the USFR, DFSS-I, DFSS-S, CGI-S, PGI-S, and DIS at baseline (or pre-injection) will be summarized within their corresponding tables indicated in the sections below.

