4.4 Efficacy Results and Tabulations

Descriptive and inferential statistics of USFR (g/minute) and changes from pre-injection at Day 1 to Weeks 4, 8 and 13, for Treatment Session 1 and from each subsequent pre-injection at Weeks 13, 26 and 39 (Treatment Session 2, 3 and 4) to 4 and 13 weeks following it respectively, will be presented for the ITT population.

Descriptive and inferential statistics of DFSS-I and changes from pre-injection at Day 1 to Weeks 4, 8, and 13, for Treatment Session 1 and from each subsequent pre-injection at Weeks 13, 26 and 39 (Treatment Session 2, 3 and 4) to 4 and 13 weeks following it, respectively, will be presented for the ITT population.

Descriptive and inferential statistics of DFSS-S and changes from pre-injection at Day 1 to Weeks 4, 8, and 13, for Treatment Session 1 and from each subsequent pre-injection at Weeks 13, 26 and 39 (Treatment Session 2, 3 and 4) to 4 and 13 weeks following it, respectively, will be presented for the ITT population.

Descriptive and inferential statistics of CGI-S and changes from pre-injection at Day 1 to Weeks 4, 8, and 13, for Treatment Session 1 and from each subsequent pre-injection at Weeks 13, 26 and 39 (Treatment Session 2, 3 and 4) to 4 and 13 weeks following it, respectively, will be presented for the ITT population.

Descriptive and inferential statistics of CGI-C at pre-injection (except for Day 1), and at Weeks 4, 8, and 13 for Treatment Session 1 and from each subsequent pre-injection at Weeks 13, 26 and 39 (Treatment Session 2, 3 and 4) to 4 and 13 weeks following it, respectively, will be presented for the ITT population.

Descriptive and inferential statistics of the proportion of the CGI-C treatment responders with much improved or better at pre-injection (except for Day 1) and at Week 4, 8, 13 weeks post injection for Treatment Session 1 and from each subsequent pre-injection at Weeks 13, 26 and 39 (Treatment Session 2, 3 and 4) to 4 and 13 weeks following it, respectively, will be presented for the ITT population.

Descriptive and inferential statistics of PGI-S and changes from pre-injection at Day 1 to Weeks 4, 8, and 13, for Treatment Session 1 and from each subsequent pre-injection at Weeks 13, 26 and 39 (Treatment Session 2, 3 and 4) to 4 and 13 weeks following it, respectively, will be presented for the ITT population.

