Descriptive and inferential statistics of PGI-C at pre-injection (except for Day 1), and at Weeks 4, 8, and 13 for Treatment Session 1 and from each subsequent pre-injection at Weeks 13, 26 and 39 (Treatment Session 2, 3 and 4) to 4 and 13 weeks following it, respectively, will be presented for the ITT population.

Descriptive and inferential statistics of the proportion of the PGI-C treatment responders with much improved or better at pre-injection (except for Day 1) and at Week 4, 8, 13 weeks post injection for Treatment Session 1 and from each subsequent pre-injection at Weeks 13, 26 and 39 (Treatment Session 2, 3 and 4) to 4 and 13 weeks following it, respectively, will be presented for the ITT population.

Descriptive and inferential statistics of DIS and changes from pre-injection at Day 1 to Weeks 4, 8, and 13 for Treatment Session 1 and from each subsequent pre-injection at Weeks 13, 26 and 39 (Treatment Session 2, 3 and 4) to 4 and 13 weeks following it, respectively, will be presented for the ITT population.

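### SAP 2.6.1 makes pre-injection severity the analysis baseline for CGI-C and PGI-C, which already rate change; this is uninterpretable under the protocol's paired t-test and conflicts with SAP 4.4

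*SAP*

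**What the plan says.** SAP 2.6.1 sets a general rule that the value at the injection visit (Day 1, Weeks 13, 26 and 39) is each session's baseline. It then adds a rule for the two change scales: "For the CGI-C and PGI-C, the corresponding severity score observed at pre-injection of each treatment session will be used as the baseline measurement".

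The same section describes CGI-C as a 7-point rating of change from the pre-injection state of the session. PGI-C is a 7-point rating of change from Day 1 or from just before the latest injection. CGI-S has 7 points and PGI-S has 8, both running from normal to most extremely ill.

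Protocol 17.9 lists the measures to be tested as "USFR change from pre-injection, CGI-C, CGI-S, PGI-C, PGI-S, and DIS change from pre-injection", followed by the two DFSS changes, and tests them as change from "pre-injection at each of the post-injection time points for the ITT population, using a paired t-test". Protocol 17 leaves the detail to the SAP: "Detailed methodology for the summary and statistical analysis of the data collected in this study will be documented in a Statistical Analysis Plan (SAP").

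SAP 2.9.1 tests "CGI-S, CGI-C, PGI-S, PGI-C, and DIS change from pre-injection, at each of the post-injection time points using a t-test". The word paired is gone, and no null value or covariate is given.

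SAP 4.4 promises "Descriptive and inferential statistics of CGI-C at pre-injection (except for Day 1), and at Weeks 4, 8, and 13 for Treatment Session 1", and likewise "Descriptive and inferential statistics of PGI-C at pre-injection (except for Day 1), and at Weeks 4, 8, and 13 for Treatment Session 1". SAP 4.3 says "Descriptive statistics of the USFR, DFSS-I, DFSS-S, CGI-S, PGI-S, and DIS at baseline (or pre-injection) will be summarized".

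**The concern.** CGI-C and PGI-C have the comparison with the pre-injection state built into the rating, so they need no baseline value. Giving them one from a different scale invites a subtraction with no clinical meaning. A paired test needs a pre-injection partner for each post-injection value. In Session 1 there is no CGI-C or PGI-C on Day 1, and the only partner the SAP names is severity.

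If that pairing is programmed, the mean difference and p-value for these two scales depend on how ill the subjects were before injection and how the categories are numbered. If SAP 4.4 is followed instead, severity does not enter. Which of these is meant should not be left to the programmer.

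**Working it through.** **Passages side by side**

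| Source | Pre-injection value for CGI-C and PGI-C | Day 1 value | Test |
|---|---|---|---|
| SAP 2.6.1 | CGI-S or PGI-S score | exists | not stated |
| Protocol 17.9 | no partner named | not addressed for the test | paired t-test |
| SAP 2.9.1 | injection visit, except Day 1 for these two scales | none | t-test, no pairing or null value |
| SAP 4.4 | the change rating itself | none | inferential statistics, unspecified |

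SAP 2.6.1 and 4.4 therefore give different pre-injection values, and disagree on whether Session 1 has one. SAP 4.4 asks for changes from pre-injection for USFR, DFSS-I, DFSS-S, CGI-S, PGI-S and DIS, but not for CGI-C or PGI-C. Its from-to phrasing for Sessions 2 to 4 also appears for the two change scales, but the word changes does not.

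**One subject.** Assume 1-7 coding. A rating of much improved (2) minus severity gives 2 - 6 = -4, 2 - 3 = -1 or 2 - 2 = 0. The same response gives three results.

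**Rejection rate of the paired reading when nothing has changed.** There is no plan figure to reproduce; SAP 2.5 takes its 187 subjects from safety-database requirements.

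From the documents: 5% significance level (SAP 2.9; taken as two-sided), n = 187 (SAP 2.5), range 120-200 (protocol 17.2).

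Assumed: coding 1-7 with 4 as no change; ratings 3/4/5 in 25/50/25% of subjects; severity SD s = 0.8, 1.0 or 1.2; correlation r = -0.3, 0 or 0.3; all subjects observed.

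- Rating SD = sqrt(0.25 × 1 + 0.25 × 1) = sqrt(0.5) = 0.707.
- SD of difference = sqrt(s² + 0.5 - 2 × r × s × 0.707). For s = 1, r = 0: sqrt(1.5) = 1.225.
- Noncentrality = shift × sqrt(n) / SD of difference, where shift is mean severity minus 4. Rejection rates come from the noncentral t with n - 1 degrees of freedom.

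| Setting | SD of difference | Mean severity 4.0 | 4.2 | 4.5 |
|---|---|---|---|---|
| n = 187, s = 1, r = 0 | 1.225 | 5.0% | 60.3% (noncentrality 2.23) | over 99.9% (5.58) |
| Lowest: n = 120, s = 1.2, r = -0.3 | 1.565 | 5.0% | 28.4% (1.40) | 93.5% (3.50) |
| Highest: n = 200, s = 0.8, r = 0.3 | 0.895 | 5.0% | 88.2% (3.16) | over 99.9% |

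The lowest and highest rows come from crossing n with every combination of s and r.

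**Other assumed inputs.** A simulation with SD 0.9 on both scales before rounding, n = 120 and 186, and 4,000 runs per setting gave paired rejection of 98-100% at mean severity 3.5, 4.5 and 5.0, and about 5% at 4.0. The one-sample test against 4 rejected in 4.3-5.6% of runs. That is expected by construction, because severity does not enter it.

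**PGI coding.** The middle of an 8-point scale is 4.5 if coded 1-8 and 3.5 if coded 0-7. With no true change the paired difference is 4 - 4.5 = -0.5 or 4 - 3.5 = +0.5. With n = 187, |t| = 0.5 / (1.225 / sqrt(187)) = 5.6, so coding alone sets the sign of a highly significant result.

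**The case against.** The strongest reply is that no single passage prescribes the subtraction. The severity sentence is in the SAP and the word paired is in the protocol. Protocol 17 hands detailed methods to the SAP, SAP 2.9.1 drops the word, and SAP 4.4 calls for no change from pre-injection on these scales. The authors may also have meant a one-sample test, treating the rating itself as the difference. This stands in part: a reader might infer that the plan definitely subtracts severity from the change rating, and the documents do not go that far. But the SAP keeps severity as the baseline in analysis and gives it no other role. No covariate or model appears in the supplied text. A one-sample or covariate analysis is not ruled out, but neither is specified.

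A reader might also infer that SAP 4.3 contradicts 2.6.1 because it omits CGI-C and PGI-C. It does not. It lists the severity scores as baselines and is silent on the change scales, which is compatible with 2.6.1.

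The rejection rates rest on assumed coding and distributions. They show direction and rough size for one reading and are not a forecast. Finally, the responder proportions for the same two scales use no severity baseline, and no sample size or interim decision depends on these tests. That limits the weight of the point but does not remove it.

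**Conclusion.** The point holds as a rule that gives a meaningless result if followed with the protocol's test, and as a direct inconsistency between SAP 2.6.1 and 4.4. It should be fixed; confidence is medium, because the unlike-scale comparison depends on the protocol's word paired.

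On that reading and the stated assumptions, the false rejection rate moves from 5% to 28-88% when mean severity is 0.2 above the midpoint, and to at least 93% when it is 0.5 above. The exact rates depend on the assumptions; the dependence on severity and coding does not.

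A reader might infer that the trial's effectiveness conclusions as a whole are in doubt. The documents do not support that. Only the t-tests on two of eight secondary effectiveness measures are exposed. The primary safety objective, CGI-S and PGI-S change, and the post-injection responder proportions are unaffected. The table shells and scale appendices were not available for this check, so nothing is claimed about them.

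**What to change.** 1. SAP 2.6.1: delete the severity-as-baseline sentence for CGI-C and PGI-C, or limit it to descriptive display of CGI-S and PGI-S.
2. SAP 2.9.1: specify a one-sample t-test of each post-injection CGI-C and PGI-C rating against the no-change category, and state the numeric coding. Keep change from pre-injection for CGI-S and PGI-S.
3. SAP 4.4: label the Week 13, 26 and 39 pre-injection ratings on these two scales as end-of-prior-session values, not as baselines for the next session. The notes to the SAP schedule of assessments already say that these visits close one session and open the next.
4. Record the departure from the paired t-test of protocol 17.9 for these two scales.
5. Clerical: in the baseline severity list of SAP 3.4, change CGI-C to CGI-S. CGI-C is not rated on Day 1, and the listing described next in 3.4 already has CGI-S.

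The cost is SAP wording and programming, with no new data. P-values for the two scales may move in either direction.

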2.6.2 Safety measures

Adverse events are recorded at each study visit, starting from the first injection of MYOBLOC on Day 1 of Treatment Session 1 and ending at study completion (i.e., 52 ± 1 week). Subjects who discontinue because of an adverse event before study completion will be contacted 13 weeks (±3 days) after their last injection of study drug to assess the adverse event. Serious adverse events, adverse events of special interest, and other immediately reportable adverse events were collected during the study period (or within 13 weeks ±3 days of last study drug injection for subjects discontinuing participation prematurely). Dental and oral health are followed closely throughout the course of the study by monitoring dental adverse events (DAE), as defined in the study protocol.

Vital signs (blood pressure, pulse, respiratory rate, and temperature) are measured after sitting quietly for at least 5 minutes at screening and each study visit, if applicable, at early termination from the study.

Subjects' suicidal ideation and behavior are measured at each study visit (including Day 1 and Weeks 4, 8, 13, 17, 26, 30, 39, 43, and 52) or, if applicable, early termination from the study, using the Columbia Suicidal Severity Rating Scale (C-SSRS). The C-SSRS baseline version (Appendix I of the protocol) will be used for Day 1, whereas the C-SSRS since last visit version (Appendix J of the protocol) will be used for all of the other visits. The C-SSRS has three subscales: suicidal ideation (Categories 1-5), suicidal behavior (Categories 6-10), and intensity of suicidal ideation. Both suicidal ideation subscale and suicidal behavior subscale have 5 yes-no categories each, with a sum score ranging from 0 to 5 and higher score indicating greater severity.

Category 1 – Wish to be Dead

Category 2 – Non-specific Active Suicidal Thoughts

Category 3 – Active Suicidal Ideation with Any Methods (Not Plan) without Intent to Act

Category 4 – Active Suicidal Ideation with Some Intent to Act, without Specific Plan

Category 5 – Active Suicidal Ideation with Specific Plan and Intent

- Category 6 – Actual Attempt
- Category 7 – Interrupted Attempt
- Category 8 – Aborted Attempt
- Category 9 – Preparatory Acts or Behavior
- Category 10 – Suicidal Behavior

The intensity of suicidal ideation has 5 items (2 are scored from 1 through 5 and the other three from 0 to 5), with a sum score ranging from 2 to 25 where higher score indicate greater risk.

For the analysis, an intensity of suicidal ideation will be defined as the maximum suicidal ideation category (1-5 on the C-SSRS) present at the assessment. A score of 0 will be assigned if no ideation is present.

Clinical laboratory tests are conducted at screening, Weeks 13, 26, as needed at the Investigator's discretion throughout the study and at study completion (i.e., Week 52) or, if applicable, at early termination from the study. Laboratory tests are analyzed by a central laboratory and include the following parameters:

Serum Chemistry:
cholesterol, phosphorus, sodium (Na ⁺), potassium (K ⁺), calcium (Ca), urea nitrogen (BUN), creatinine, albumin, total protein, aspartate transaminase (AST), alanine transaminase (ALT), alkaline phosphatase (ALP), gamma-glutamyl transferase (GGT), uric acid, total bilirubin, glucose, and lactate dehydrogenase (LDH).
Hematology:
hemoglobin, hematocrit, platelet count, red blood cell (RBC) count, MCV, MCH, MCHC, white blood cell (WBC) count, WBC differentials (%), including bands, neutrophils, lymphocytes, monocytes, eosinophils, and basophils
Urinalysis:
specific gravity, pH, glucose, blood, protein, color, nitrites, ketones, bilirubin, urobilinogen, and leukocyte esterase.

A complete physical examination is performed at screening, Weeks 4, 13, 26, 39, and at study completion (i.e., Week 52) or, if applicable, at early termination from the study. The complete examination will involve gross examination of general appearance; head, ears, eyes, nose and throat; skin; extremities; chest; abdomen; and lymph nodes. Cardiac and pulmonary auscultation and measurement of vital signs and weight will also be conducted as part of the complete physical exam. A brief physical examination, consisting of cardiac and pulmonary auscultation is performed on Day 1 prior to injection of study drug and at Weeks 8, 17, 30, and 43. Height will be recorded at screening only. Lung functioning is measured for subjects with ALS, using forced vital capacity (liter) (FVC), and in other subjects if warranted, at the discretion of the Investigator at screening, before the first injection of study drug on Day 1, at Weeks 4, 8 (as clinically warranted), and 13. Thereafter, FVC will be checked if warranted at Investigators' discretion (such as if the subject has ALS). If any of the Physical Exam findings were abnormal and clinically

significant prior to treatment, the event was recorded as medical history, while if occurred after treatment they event was recorded as an Adverse Event.

A neurologic exam is performed at screening, on Day 1 prior to injection of study drug, at Week 13, as needed at the Investigator's discretion throughout the study, and at study completion (i.e., Week 52) or if applicable, at early termination from the study. The neurologic exam consists of 9 sections to evaluate: 1) level of consciousness; 2) speech; 3) cranial nerves; 4) motor; 5) sensory; 6) coordination; 7) gait; 8) reflexes; and 9) Romberg test (Appendix G of the protocol).

A dental exam is performed by a licensed dentist (DDS or DMD) at screening, at Weeks 4, 13, 26, as needed at the Investigator's discretion throughout the study and at study completion (i.e., Week 52) or, if applicable, at early termination from the study.

Findings of dental exam that meet the DAE criteria as defined in the protocol will be reported as such. Subjects or their caregiver will also complete a dental questionnaire at screening.

An oral exam (Appendix H of protocol) is performed by the Investigator at each study visit where a dental exam is not planned by protocol.

Findings of the oral exam that meet the DAE criteria as defined in the protocol will be reported as such.

A urine pregnancy test is performed on all females of child-bearing potential at screening, on Day 1 (before the first injection of the study drug), as needed at the Investigator's discretion throughout the study, and at study completion (i.e., Week 52) or, if applicable, at early termination from the study.

